10. STUDY MEDICATION AND MANAGEMENT

10.1. Description of Study Drug

The study medication for this study is ATI-502 Topical Solution, 0.46%. It is a clear, colorless to light pink solution. The inactive ingredients include: purified water, transcutol P, propylene glycol, PEG400, dimethyl sulfoxide (DMSO), kolliphor CS 20, benzyl alcohol, poloxamer 188, and povidone K30.

Table 3: Investigational Product

STUDY MEDICATION INFORMATION	
Study medication name	ATI-502
Dosage Strength	0.46%
Manufacturer	PMRS, Inc., Horsham, PA
Pharmaceutical Form	Topical Solution
Container	Amber Glass Bottle, 120 mL with screw cap
Storage Conditions	59°F to 77°F (15°C to 25°C)
Dose regimen	
Route	Topical
Frequency	Twice-daily
Duration of administration	4 weeks
Other supplies	Disposable, single-use droppers will be provided.

10.2. Subject Randomization

This is an open label study therefore, no randomization schema will be generated for this study. All subjects will receive open label ATI-502 Topical Solution, 0.46%.

10.3. Study Drug Packaging, Labeling and Storage

The study medication must be used by the study subjects only. Investigational site staff will explain the application of the study medication to subjects.

Study medication will be provided by Aclaris Therapeutics, Inc. and labeled according to regulatory requirements. Study medications must be stored in a secure area with limited access under appropriately controlled and monitored storage conditions. Study medication should be stored at controlled room temperature 59°F - 77°F (15°C – 25°C). Subjects will be instructed to store the study medication in the original glass bottle (in the carton provided) at room temperature, away from heat, moisture, direct light, and to keep it from freezing and out of the reach of children.

The study medication will be supplied in amber glass 120 mL bottles. Disposable droppers with 1 mL calibration mark will be provided to the investigational sites for dispensing to enrolled subjects.

Study drug for this study is ATI-502 Topical Solution 0.46%. The study medication will be supplied to subjects enrolled to the study at Visit 2.

10.4. Study Drug Accountability and Disposal

The Principal Investigator or designee is responsible for ensuring accountability for the investigational agent, including reconciliation of medications and maintenance of medication records. Upon receipt of study medication, the clinical site will check for accurate delivery and acknowledge receipt by signing (or initialing) and dating the documentation provided. One copy of this document will be returned to Aclaris Therapeutics, Inc. (or designee) and one copy will be maintained in the study file at the site. In addition, an accurate study medication disposition record will be kept, specifying the amount dispensed for each subject and the date of dispensing. This inventory record will be available for inspection at any time. At the completion of the study, the original inventory record will be available for review by Aclaris Therapeutics, Inc. upon request. Final medication accountability will be performed by the study monitor at the completion of the study and all used and unused study medication bottles will be returned to Aclaris Therapeutics, Inc. or designee for disposal.

10.5. Additional Clinical Supplies

In addition to the study medication supplies, each site will be supplied with the following clinical supplies to conduct the study:

- Disposable study medication dispensing droppers
- Insulated bags for subjects to transport study medication supplies
- Canfield photography equipment
- Central laboratory testing kits

11. TREATMENT OF SUBJECTS

11.1. Identification of Target Treatment Area

At Visit 1 and Visit 2, the investigator will identify a target treatment area(s) that meets all inclusion criteria (e.g. a diagnosis of AD based on the criteria of Hanifin and Rajka, BSA between 2-20%, and a PGA score of 3 or 4). The target treatment area can not include the scalp, face, palms of hands, soles of feet, groin or genitalia. The investigator will record the identified target treatment area on the body map in the subject's source documents and eCRF. These target treatment areas will be photographed at each specified protocol time point (Refer to [Table 2](#)). Sites will use colored stickers to mark the treatment areas prior to the photographs being taken. (Refer to Section [12.6](#) for photography instructions)

If new areas of atopic dermatitis develop while the subject is on study, these areas may be treated with the ATI-502 study medication (excluding the face, scalp, soles of feet and palms of hands). The treating investigator must identify these new treatment areas at a treatment visit (Visit 2, 3 or 4) to ensure that the area meets the protocol defined treatment criteria. These new treatment areas will be documented in the subject's source documents and in the eCRF.

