9. SELECTION AND WITHDRAWAL OF SUBJECTS

9.1. Subject Inclusion Criteria

Subjects must meet the following criteria to be eligible for participation in the study:

1. Able to comprehend and willing to sign an Informed Consent Form (ICF).
2. Male or non-pregnant, non-nursing female subjects ≥ 18 years old at the time of informed consent.
3. Subject must have diagnosis of AD according to the Hanifin and Rajka criteria.
4. Subject must have a diagnosis of moderate (PGA =3) or severe (PGA=4) AD for a period of ≥ 6 months prior to the first dose of study medication (Visit 2).
5. Subject Visit 1 photographs are approved for enrollment by the dermatology review panel.
6. Body surface area involvement must be between 2-20% (excluding scalp, face, palms of hands, soles of feet, groin and genitalia).
7. Subject must have an absolute neutrophil count (ANC) and a platelet count within normal limits
8. Subject must be willing to refrain from washing area of treatment or swimming for 6 hours after each treatment application with ATI-502.
9. Subjects must be willing to refrain from excess of sun exposure.
10. Subject is willing and able to follow all study instructions and be willing to attend all study visits.
11. Subject must refrain from participating in strenuous exercise that would cause profuse sweating for a period of 6 hours after each treatment application with ATI-502.
12. Subject must refrain from using moisturizers, emollients, and sunscreen on target AD treatment area for the duration of protocol therapy.
13. Be in good general health and free of any known disease state or physical condition which, in the investigator's opinion, might impair evaluation of the subject or which might expose the subject to an unacceptable risk by study participation.
14. If a woman of childbearing potential (WOCBP), must have a negative serum pregnancy test at Screening (Visit 1) and a negative urine pregnancy test at Baseline (Visit 2) and agree to: use a highly effective method of birth control for the duration of the study; not be planning a pregnancy during the study duration and use contraception for 30 days after last application of study medication.
15. Sexually active male subjects must agree to use a barrier method of contraception from the first application of study medication to at least 30 days after the last application of study medication.

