19. APPENDICES

APPENDIX 1. SUBJECT INSTRUCTIONS

Preparation and General Instructions:

1. Gather a clean washcloth and towel, the study medication bottle, and disposable dropper.
2. Skin should be clean and dry before applying study medication.
3. Refrain from bathing, swimming and/or participating in strenuous exercise that would cause profuse sweating for 6 hours after application of study medication.
4. Refrain from applying moisturizers, emollients and sunscreen to AD treatment areas for the duration of protocol therapy. Moisturizers, emollients and sunscreens may be applied to non-AD treatment areas.
5. Wash your hands with soap and water before and after using this study medication.
6. Apply a thin layer of study medication to the identified AD target skin area as instructed by the study doctor or the study staff. Keep applying study medication to the area throughout the study, even if the skin begins to clear. If new areas of AD appear, study medication may be applied to these areas.
7. Avoid study medication contact with the eye.
8. You will apply study medication twice-a-day, approximately 12 hours apart.
9. Remember to bring your study medication bottles both used and unused to each study visit.

Study Medication Application:

1. Draw up exactly 1 mL of study medication into the dropper. The medication level should be at the 1mL line.
2. During study medication application, avoid any study medication running into your eyes.
3. Squeeze a few drops of study medication onto the center of the identified target AD area and gently rub the study medication into your skin. Keep applying a few drops and rubbing into your skin until **the entire area** is covered with a thin film of study medication.
4. Draw up additional medication - 1 mL at a time- to cover the entire AD area.
5. Replace the screw top cap and make sure it is closed tightly. Dispose of the used dropper(s).
6. It is important to continue to apply study medication to the target AD areas throughout the study, even if the skin begins to clear.
7. Wash your hands after using this product to prevent any residue being left on your hands.
8. If you missed a dose or doses, tell the study staff at your next visit.

Missed Doses: If you miss a dose of this study medicine, apply it as soon as possible. However, if it is almost time for your next dose, skip the missed dose, and go back to your regular dosing schedule.

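### Protocol 11.1 bars six body sites for target areas but lists only four for new areas, and the Appendix 1 subject instructions allow new areas to be treated with no site limit and no wait for the investigator

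*Protocol*

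**What the plan says.** Protocol 11.1 sets the rule for target areas: "The target treatment area can not include the scalp, face, palms of hands, soles of feet, groin or genitalia". Inclusion criterion 6 (Protocol 9.1) names the same six sites, although there they limit the body surface area counted for eligibility: "Body surface area involvement must be between 2-20% (excluding scalp, face, palms of hands, soles of feet, groin and genitalia".

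The next paragraph of 11.1 deals with lesions that appear during the study and gives a shorter list: "these areas may be treated with the ATI-502 study medication (excluding the face, scalp, soles of feet and palms of hands". It adds a control: "The treating investigator must identify these new treatment areas at a treatment visit (Visit 2, 3 or 4". The stated purpose is to check the area against treatment criteria defined in the protocol, and identified new areas go into source and the eCRF.

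Appendix 1, general instruction 6, is addressed to the subject. It begins: "Apply a thin layer of study medication to the identified AD target skin area as instructed by the study doctor or the study staff". Its new-area sentence reads: "If new areas of AD appear, study medication may be applied to these areas". The only anatomical cautions in the appendix concern the eyes: "Avoid study medication contact with the eye" and "During study medication application, avoid any study medication running into your eyes".

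**The concern.** There are two mismatches.

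First, within 11.1, groin and genitalia are barred for target areas but missing from the list for new areas. The reference to treatment criteria may bring them back in, but 11.1 does not say which criteria apply to a new area. Two investigators could reasonably decide differently about a new groin lesion.

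Second, the subject-facing text carries neither of the controls in 11.1. It names no barred site and does not tell the subject to have the investigator identify the area. The phrase about following staff instruction belongs to the sentence on the identified target area; the new-area sentence has no such qualifier. Neither eye caution bars the face.

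Safety and tolerability is the primary outcome, so where the drug is applied matters. Protocol 13.3.3 lists the location of an event among the factors for judging causality. If a subject treats an area that the site has not identified, the investigator may have to judge a local event without a treatment record for that location.

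**Working it through.** The plan states no figure on this point, so the check is a comparison of text followed by a simple bound.

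**Site lists**

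| Text | Sites barred | Investigator identification |
|---|---|---|
| Protocol 11.1, target areas | 6: scalp, face, palms, soles, groin, genitalia | Yes, Visits 1 and 2 |
| Protocol 11.1, new areas | 4: face, scalp, soles, palms | Yes, Visit 2, 3 or 4 |
| Appendix 1, new areas | 0 | Not mentioned |

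The difference within 11.1 is 6 − 4 = 2 sites (groin and genitalia). Appendix 1 names 0 of the 6.

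**Where new-area treatment is allowed.** Six places in the protocol allow it: the synopsis, 7.1, Table 2 footnote 10, 11.1, 11.2 and Appendix 1. Only 11.1 attaches a site limit or an identification step. For the four other than 11.1 and Appendix 1 this is ordinary drafting, because site staff hold 11.1. Appendix 1 differs because it speaks to the subject.

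**Upper bound for one lesion treated before the next listed identification visit.** Inputs are twice-daily application (11.2) and the visit days and ±3-day windows in Table 2. Applications = days between visits × 2.

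- Visit 2 (Day 1) to Visit 3 (Day 8), nominal: 7 × 2 = 14.
- Visit 3 (Day 8) to Visit 4 (Day 15), nominal: 7 × 2 = 14.
- Visit 2 (Day 1) to a late Visit 3 (Day 11): 10 × 2 = 20.
- An early Visit 3 (Day 5) to a late Visit 4 (Day 18): 13 × 2 = 26.

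A lesion that appears after Visit 4 (Day 15) has no later identification visit listed. About 14 days then remain to the end of dosing (29 − 15 = 14, taking the nominal Visit 5).

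These are ceilings for one lesion, not estimates of exposure. The documents give no rate of new lesions, so no expected number of affected subjects can be derived.

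**What other records would show.** BSA and SAD do not assess new areas (12.2, 12.4). Photographs are of target areas (12.6). EASI covers whole regions, including head and neck and the genital area, but does not record which areas were treated (12.3). Exposure is summarized by duration, weight and volume, with no body site (SAP 4.1.7). The record of a treated new area is therefore the entry that 11.1 requires once the area is identified.

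**Effect on the analysis.** Adverse events are tabulated by system organ class and preferred term, not by body site (SAP 4.3.1). No planned table changes.

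**The case against.** The strongest reply is that the controls exist and the subject is in regular contact with staff who know them. Table 2 schedules subject instruction at Visits 1 to 5, and footnote 11 requires the site to go over proper application. Staff explain application (10.3), and 11.7 adds questioning and counselling on compliance. Identified new areas are recorded in source and the eCRF. All of this stands and narrows the gap. It does not close it: the reminders listed in footnote 11 cover sweating, bathing, swimming and moisturizers, not barred sites or new areas.

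The shorter list may also be deliberate, or may already be covered by the treatment criteria. Either is possible. The documents give no reason for the difference, and an explicit four-site list beside a six-site list does not tell the investigator which one governs.

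Finally, 11.1 requires identification at a visit but does not expressly require it before the first application. Prior confirmation is the natural reading, since the purpose is to ensure that the area qualifies, but it remains a reading.

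A reader might infer more than the text supports:

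- *That the protocol authorizes groin or genital treatment.* It does not say so; it leaves the point unclear.
- *That treated new areas go unrecorded in general.* Once identified, they are recorded.
- *That subjects rely on Appendix 1 alone at home.* Its wording makes home use plausible, but no section says how it is issued, and the consent pages are not available to check.

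**Conclusion.** The point holds as a minor one. The mismatch in the text is certain: two of six sites are missing from the new-area list in 11.1, and Appendix 1 has neither a site limit nor an identification step. A subject who followed Appendix 1 exactly could apply the drug to a site that 11.1 bars, such as the face, or to an area not yet identified.

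The consequence is limited to local safety, and to attribution of local adverse events in areas treated before or without identification. It would be tempting to conclude that the primary safety analysis is compromised. The documents do not support that: the planned summaries are unaffected, and the number of subjects involved is unknown and could be none.

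The conclusion assumes that subjects receive Appendix 1 as written and that 11.1 intends identification before treatment. If staff routinely state the limits orally, the practical risk is smaller, but the written conflict remains.

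**What to change.** 1. In Protocol 11.1, apply the six-site exclusion to new areas. If groin and genitalia are deliberately allowed there, say so.
2. In Appendix 1, replace the new-area sentence. Suggested wording: *If a new patch of eczema appears, do not treat it until the study doctor has confirmed it. Never use the study medication on the face, scalp, palms, soles, groin or genitals.* The site list should match whatever 11.1 finally says.
3. Allow confirmation at an unscheduled contact or visit, and extend the visit list in 11.1 to match, so that lesions arising between visits or after Visit 4 are not left untreated. This matters because 11.6 prohibits other topical treatments for atopic dermatitis.

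The cost is IRB approval of the revised protocol text and subject instructions (17.1), plus occasional unscheduled contacts. Without unscheduled confirmation, a subject would wait about 7 days at nominal spacing and up to 13 days with visit windows. A lesion arising after Visit 4 would go untreated for about 14 days, to the end of dosing. Endpoints, populations and planned analyses do not change.

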11.2. Application of Investigational Product

Subjects will be instructed to apply a thin film of ATI-502 Topical Solution 0.46%, twice-daily - once in the morning and approximately 8-12 hours later - to the identified target AD areas. The ATI-502 study medication should be applied to clean dry skin. The subject must wash her/his hands thoroughly before and after each study drug application. If new areas of AD develop while the subject is on study, ATI-502 study medication may be applied to these sites.

Investigational site staff will dispense 2 bottles of study medication along with disposable droppers to the subject Visit 2. Subsequent study drug dispensing will be determined by the site based on the amount used between visits. Study medication bottles will be weighed by the site staff at the time of dispensing and when the bottles are returned. Subjects are to return used and unused study medication at each study visit so that the bottles can be weighed. Sites can re-dispense partially used bottles of study medication at a visit. The disposable droppers should be disposed of at the subject's home.

11.3. Study Medication Interruption

Treatment with ATI-502 Topical Solution, 0.46% should be temporarily interrupted in the event of severe adverse events considered related to ATI-502 Topical Solution, 0.46%, or in the event of one or more of the abnormal laboratory values in [Table 4](#).

Table 4: Study Medication Interruption Criteria

Laboratory Test	Hold Study Medication if:	Resume Study Medication if:
WBC count	$< 2 \times 10^9/L$	$\geq 2.5 \times 10^9/L$
ANC	$< 1 \times 10^9/L$	$\geq 1.5 \times 10^9/L$
Lymphocyte count	$< 0.5 \times 10^9/L$	$\geq 0.75 \times 10^9/L$
Platelet count	$< 75 \times 10^9/L$	$\geq 100 \times 10^9/L$

Hemoglobin	< 8 g/dL or a decrease > 2g/dL	≥ 10 g/dL
AST or ALT	> 3 x ULN	< 2 x ULN or within 20% of Baseline values
Serum creatinine	>2 x ULN	<1.5 x ULN or within 10% of Baseline value

If a subject has one or more of the abnormal laboratory values noted in [Table 4](#), the investigator or designee upon receipt and review of the central laboratory report should instruct the subject to hold study medication applications. The investigator or designee should ask the subject about symptoms, concomitant illnesses and medications and repeat the test(s) as soon as possible. The Medical Monitor must be notified of dose interruptions due to SAEs considered related to study medication or laboratory abnormalities noted in [Table 4](#).

If the retest confirms the abnormal laboratory value, then the study medication should continue to be held followed by repeat testing once a week or sooner at the discretion of the investigator. The subject should be followed until the laboratory abnormality(s) returns to normal or to baseline values.

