⁷ All subjects will be required to have virology testing for HepB (HBsAG), HCV(antibody), and HIV (antibody). If a subject demonstrates to have serological evidence HepB (HBsAG), HCV (antibody) or HIV (antibody), the subject will not be allowed to enroll to the study.

⁸ Canfield staff will review all photographs within 2 days of the photographs being submitted. If a re-take is required, Canfield will notify the site and the re-take photographs will need to be performed within 7 days of the visit. Prior to enrollment to the study, each subject's Visit 1 photos will be reviewed by a panel of board certified dermatologists to ensure that the subject's target areas for treatment meet the study entry criteria. In cases where the photographs do not properly characterize the disease (due to flashback and whitening on the photographs) the subjects will be allowed to enroll to the study based upon the Principal Investigator's clinical assessment of the subject.

⁹ At visit 2, following confirmation that the subject is approved for enrollment to the study, the site will weigh and dispense supplies of ATI-502 study medication and disposable droppers to the subject for at home application of the study medication.

¹⁰ All subjects will have their first application of study medication applied in the clinic during Visit 2. Subjects will continue to apply ATI-502 Topical Solution, 0.46% to all target areas twice a day for 4 weeks (Day 28) unless the subject meets the criteria for treatment interruption. If new areas of AD develop, subjects will be allowed to treat these areas with the ATI-502 study medication.

¹¹ Sites will be required to review with each subject the proper application of the study medication and remind that they must refrain from exercise that may cause excessive sweating, bathing or swimming for a period of 6 hours after the application of study medication. Subjects are also to be reminded that they may not apply moisturizers, emollients, or sunscreen to target AD areas during protocol treatment.

¹² All non-serious AEs will be collected from the time of first study medication application until the final study visit. Serious AEs will be collected from the time of consent through the final study visit.

¹³ A final safety follow up visit will be conducted at week 8 (Visit 6). For those subjects that discontinue the study early, they must return to the clinic 4 weeks following the last study medication application for a final safety visit.

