13.1.5. Pregnancy Testing

Subjects who are WOCBP must have a negative serum pregnancy test result at Screening (Visit 1) to continue in the study, and a negative UPT at Baseline (Visit 2) prior to study entry. If the result of any post-treatment urine pregnancy test is positive, the subject will be withdrawn from the study and the subject’s pregnancy documented and followed. In addition, the investigator or designee will perform a urine pregnancy test for subjects who are WOCBP at Visit 6 (Post Treatment Safety Follow Up Visit).

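### Protocol Table 4: the hemoglobin resume limit of 10 g/dL does not answer the hold for a fall of more than 2 g/dL, so above a baseline of 12 g/dL one value can meet both columns

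*Protocol*

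**What the plan says.** Protocol section 11.3 interrupts treatment for severe related adverse events or for any laboratory value in the hold column of Table 4. For hemoglobin the hold column reads "< 8 g/dL or a decrease > 2g/dL" and the resume column gives only a floor of 10 g/dL. The row does not say what the decrease is measured from.

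The text after the table sets the sequence. The investigator or designee "upon receipt and review of the central laboratory report should instruct the subject to hold study medication applications", and the test is repeated as soon as possible. Then: "If the retest confirms the abnormal laboratory value, then the study medication should continue to be held". Further tests come at least weekly. Follow-up continues until the value is normal or back at baseline, and the Medical Monitor must be told of interruptions for Table 4 abnormalities.

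Other rows treat recovery differently. The AST/ALT row resumes at "< 2 x ULN or within 20% of Baseline values", and the creatinine row also has a limb tied to Baseline. The permanent discontinuation limits for hemoglobin in section 9.3 are absolute: below 6.5 g/dL, or a second value below 8 g/dL.

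**The concern.** A hold rule and its resume rule should not both be true of the same value. Here they can be, because a large fall from a healthy baseline may still end above 10 g/dL. The sentence on confirmed values keeps such a subject off drug, while the resume cell taken alone lets the subject restart at the very value that triggered the hold.

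At stake are subject protection and consistent dosing at about 6 sites, in a study whose primary outcome is safety and tolerability. The estimates and summaries in the SAP are not at stake.

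**Working it through.** **Inputs.** From Table 4: hold if Hb < 8 or if B − Hb > 2; resume if Hb ≥ 10 (all in g/dL). B is the reference for the decrease, taken here as Baseline. That is an assumption, since the row names no reference. The documents give no baseline hemoglobin values, so a range of B is shown.

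**Overlap.** The limb below 8 can never coincide with 10 or more. The relative limb can. Both columns are met when 10 ≤ Hb < B − 2, which needs B − 2 > 10, so B > 12.

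| Baseline B | Relative hold applies below B − 2 | Values meeting both columns |
|---|---|---|
| 12 | 10 | none |
| 13 | 11 | 10 to just under 11 |
| 14 | 12 | 10 to just under 12 |
| 15 | 13 | 10 to just under 13 |
| 16 | 14 | 10 to just under 14 |

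Worked case: B = 15 and Hb = 12.5. The fall is 15 − 12.5 = 2.5 > 2, so hold is met. Also 12.5 ≥ 10, so resume is met. A retest of 12.5 confirms the abnormality, and the text says to keep holding.

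**Other rows.** WBC (hold below 2, resume at 2.5), ANC (1 and 1.5), lymphocytes (0.5 and 0.75) and platelets (75 and 100), all × 10⁹/L, leave gaps of 0.5, 0.5, 0.25 and 25. They cannot overlap. If the limbs tied to Baseline are read as up to 1.20 × and 1.10 × Baseline, AST/ALT can overlap only if Baseline exceeds 3/1.20 = 2.5 × ULN, and creatinine only if it exceeds 2/1.10 = 1.82 × ULN. Hemoglobin is the only row that overlaps without an already raised baseline.

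**Does another section settle it?** Section 9.3 does not, because its hemoglobin limits are absolute and lie below 10 g/dL.

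**Low baselines.** Inclusion 7 says "Subject must have an absolute neutrophil count (ANC) and a platelet count within normal limits" and sets no hemoglobin limit, so B below 10 is possible. With B = 9.5, a subject held at a value below 8 who returns fully to 9.5 still fails the 10 g/dL floor. This is a separate gap in the same cell.

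**Ceiling on treatment days.** Dosing runs "twice a day for 4 weeks (Day 28) unless the subject meets the criteria for treatment interruption". With the ±3-day visit windows in Table 2, the earliest Visit 3 sample is Day 8 − 3 = 5 and the earliest Visit 4 sample is Day 15 − 3 = 12. Days that could differ between the two readings are at most 28 − 5 = 23 and 28 − 12 = 16, less the time to report and retest. The documents do not give that time. These ceilings also require that the fall has not recovered by Day 28.

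**Check of the fix.** Requiring Hb ≥ 10 and B − Hb ≤ 2 to resume cannot coincide with B − Hb > 2 or with Hb < 8, so no value meets both columns at any baseline.

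**The case against.** The best reply is that section 11.3 already decides the case. A fall that is still more than 2 g/dL is still a Table 4 abnormality at every later test. Restarting on it would trigger the hold again from the same report, so the sensible reading is that the resume cell applies only once the hold condition has cleared. Every such hold also reaches the Medical Monitor, which limits differences between sites.

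Most of this stands. A reader might infer from the overlap that the protocol has no rule for these subjects. The documents do not support that, because the sentence on confirmed values is a rule and it points to holding. What remains is that the resume cell does not say so. On the sensible reading the true threshold is the higher of 10 and baseline minus 2, and the cell gives only the first. Notification brings each case to view but does not write the restart criterion.

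The unnamed reference is a weaker point. Section 13.1.5 calls for "a negative UPT at Baseline (Visit 2) prior to study entry", Table 2 labels the same visit Baseline, neighbouring rows use the term, and SAP section 4.3 defines the laboratory baseline as the last non-missing value on or before the date of first application. Naming it in the row is a tidy-up.

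**Conclusion.** The concern holds as a minor defect. For baselines above 12 g/dL the two hemoglobin cells overlap from 10 g/dL to just under baseline minus 2. The surrounding text favours holding, but the resume cell read literally permits restart without recovery.

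It would be tempting to conclude that many subjects, or most of the 4-week course, are exposed to conflicting instructions. The documents do not show this. How many of the 30 planned subjects would have a fall above 2 g/dL cannot be derived and may be few. The 23-day and 16-day figures are ceilings for a single unrecovered case, not expected losses. No endpoint, population or planned analysis changes. The initial hold, the retest, the limb below 8 g/dL and the discontinuation limits work as written. The result assumes that the decrease is measured from Baseline.

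**What to change.** Amend the hemoglobin row of Table 4:

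- **Hold:** below 8 g/dL, or a decrease of more than 2 g/dL from Baseline.
- **Resume:** at least 10 g/dL and no longer more than 2 g/dL below Baseline.
- **Optional:** if Baseline was below 10 g/dL, the Medical Monitor may agree resumption on return to Baseline, since the 10 g/dL floor otherwise bars restart even after full recovery.

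The cost is one table row in an amendment and a note to sites, with no new tests. The downside is that a few subjects may be held longer in a 4-week course. For baselines above 12 g/dL the new row leaves no margin between hold and resume, unlike the blood-cell rows. A tighter recovery margin is a choice for the medical team and is not needed to remove the overlap.
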